### *For Exploratory Endpoint – Brain and Cognition*

*Brain MRI.* Participants will receive brain MRI scans conducted on a 3-Tesla MRI system (Siemens Prisma) at Toronto Neuroimaging Facility (ToNI) of University of Toronto, instead of the scanner at CAMH, a MRI GE Discovery 750 scanner. This design is planned because the required fMRI sequence is not available on CAMH's scanner. Specifically, we will collect the functional data using the multi-echo multiband sequence (Cohent et al., 2017), which is not collectable from the MRI scanner of CAMH. Multi-echo multiband fMRI outperforms single-echo multiband fMRI (which is collectable from the MRI scanner of CAMH) in data quality and better denoising (Kovářová et al., 2021; Cohen et al., 2021). At the same time, the multi-echo multiband sequence can still preserve high spatial and temporal resolution. fMRI data quality is grossly impaired by the noises introduced by excessive in-scanner head motion, which is usually more pronounced in autistic and other neurodevelopmental populations. Taken together, the multi-echo multiband sequence available at the TONI should be fitter for the present targeted participants than any available fMRI sequences at the CAMH. Our proposed fMRI acquisition has been rigorously tested and applied safely to autistic populations across the wide age ranges (King et al., 2018; Lin et al., 2022). The acquisition parameters of T1-weighted and diffusion MRI (dMRI) will use Human Connectome Project-like and Adolescent Brain Cognitive Development (ABCD) study-like data acquisition with multiband excitations to reduce scan time, facilitating successful scanning. An additional pulse sequence includes a study-specific implementation of Siemen's H-MR spectroscopy (MRS).

These sequences are considered investigational and ToNI has obtained them as a "Work in Progress" (WIP) through a contract with Siemens. To comply with the contract, the consents include language indicating that investigational methods are being used, that there is no additional risk, and that anonymized data may be shared with collaborators. When these sequences become part of the "stock" sequences available on the scanner, we will update the consents. This research project uses investigational MRI research techniques provided by the manufacturer that are not available on clinical MRI scanners. These research scans are performed under strict safety guidelines and do not pose any additional risk to the participant. We will ask each participant for their permission to use these new research MRI methods for this project. MRI data may be shared with Siemens, the manufacturer, for ongoing improvement and quality assurance but participant name and other identifying information will not be included.

For the main clinical trial: participants will receive two brain MRI scans, respectively, at V2 and V5. This MRI session for the main clinical trial will consist of a T1-weighted image (around 6 mins), fMRI (around 20 mins, divided into two scans), diffusion MRI (around 9 mins), and MRS (around 10 mins), with around 45 mins scanning in total.

For the optional dense sampling brain MRI data collection: participants will receive additional eight brain MRI scans consisting of a T1-weighted image (around 6 mins), fMRI (around 14 mins) with around 20 mins scanning in total.

There will be ToNI-specific informed consent forms, ToNI-specific recruitment materials, screening form for MRI scans at ToNI, and ToNI general protocol, as requested by ToNI's policies (<https://toni.psych.utoronto.ca/policies/#6>). These materials are attached in appendix H (Appendix H1-H4). Participants will read these materials and sign on the ToNI-specific informed consent forms (Appendix H1a and H1b) and screening form (Appendix H2).

*Avoid/Escape Go/No-Go task.* This Avoid/Escape Go/No-Go task employs a 2 × 2 (Go/No-go × Avoid/Escape) factorial design. On every trial, the agent is presented with one of four cues. Two of the cues are always paired with an aversive sound (Escape condition) while the other two are paired with silence (Avoid condition). The agent’s goal is to learn, for each cue, which response (active Go or passive No-go) more frequently results in silence during feedback. For ease of reference, we will refer to the responses that maximize the frequency of silence during the feedback as the “correct” responses throughout the paper. This means that in the Avoid condition, correct responses will prevent the aversive sound from playing, while in the the Escape condition, correct responses will stop the aversive sound that is already being played. The feedback is probabilistic, which means that even “correct” responses will sometimes lead to experiencing the aversive sound. Probabilistic feedback introduces uncertainty and makes it more challenging to learn, which response is correct. We will then use an active inference scheme to model how the proposed perturbations lead to hopelessness, increased Pavlovian control and increased active-escape bias. This task and model have been validated by Co-Investigator [name] to provide computational hypothesis space for understanding suicidal thoughts and behaviours in neurotypical populations (Karvelis & Diaconescu, 2022).

### **6.1.2.1 Outline of Study Procedures of Main Clinical Trial**

#### ***Visit 1 (V1) – Screening Visit***

- Administered by trained study staff:
  - Informed consent
  - Review of medical history, family medical history, and demographics
  - ATHF
  - Vital Signs (blood pressure, pulse)
  - Height and weight
  - ADOS-2
  - Nine-item form of RSPM
  - UKU Side Effect Scale
  - Self-rated questionnaires: AQ-12, RBQ-2A, CAT-Q, SBQ-ASC
- Clinician administered:
  - SCID-5-CV
  - GRID-HAMD-17
  - Review of prior and current medications; the participant will be tapered from prohibited medications (see Section 5.6), if any, under the supervision of the study clinician
    - The study clinician will discuss options of tapering off medications with the participant and their healthcare provider.
    - Participants will be given a choice of how quickly they would like to come off the medications, but participants must be off concomitant medications (see Section 5.6) at least 2 weeks prior

- to the Baseline Visit (V2). Some medications (e.g., fluoxetine) may require a longer tapering period (at least 4 weeks).
- Review of eligibility criteria, medical history, and family medical history
  - Review of assessments
  - Documentation of contraceptive method to be used by the participant
  - Biological specimen collection and laboratory evaluations collected at the Queen Street CAMH laboratory:
    - Clinical laboratory tests:
      - Approximately 20 mL blood will be drawn to conduct the following evaluations:
      - *Haematology:* hemoglobin, hematocrit, red blood cell count, mean corpuscular hemoglobin, mean corpuscular volume, mean corpuscular hemoglobin concentration, white blood cell count (with differential), and platelet count.
      - *Chemistry:* albumin, alkaline phosphatase, alanine aminotransferase (ALT), amylase, aspartate aminotransferase (AST), bicarbonate, bilirubin (direct, indirect, and total), calcium, chloride, creatine kinase, creatinine, gammaGT, glucose, lactate, dehydrogenase, lipase, magnesium, phosphate, potassium, protein-total, sodium, urea (blood urea nitrogen), and uric acid.
    - Urine Samples:
      - *Urinalysis:* a dipstick urinalysis will be performed for blood, glucose, ketone, protein, pH, specific gravity, nitrite, leukocytes, bilirubin, and urobilinogen
      - *Urine drug screen:* for illicit drugs or drugs of abuse. Results of a positive drug screen will be reviewed by the study clinician for pattern of use.
      - *Urine pregnancy test* for all women of childbearing potential
    - ECG: Standard 12-lead ECG to check heart function

### **Washout Period: Minimum of 2-Weeks**

Participants who are on concomitant medications (Section 5.6) must be tapered off at least 2 weeks prior to Baseline (V2). The plan for tapering off medications will be determined at the first screening visit (V1) with the participant and the study physician. During the washout period, the study physician will have weekly appointments with the participant to check how they are doing and ensure they are safe. The weekly appointments can be scheduled in-person or remote (via telephone/WebEx) based on the participant's preference and at the discretion of the study physician. Participants will be assessed for suicidality with the SBQ-ASC at each contact/visit.

Any safety assessment visits during the washout period will be called V1a, V1b, etc. During these visits, the SBQ-ASC and any changes in medications since the previous visit will be obtained in addition to other assessments at the study clinician's discretion.

### **Visit 2 - Baseline Visit (V2) - Day -15 to Day -8**

The Baseline visit (V2) will occur approximately 3-6 weeks after the initial Screening (V2) when the participant has successfully been tapered off any concomitant medication. At the Baseline Visit (V2), the participant's eligibility will be confirmed by the study investigator by reviewing the Inclusion/Exclusion Criteria (Section 4.4) and updating the medical history. The Baseline visit (V2) can occur within 7 days before the anticipated psilocybin session and may be split over multiple days to reduce the burden on the participant (additional study visits will be labelled V2a, V2b, etc.). The self-rated questionnaires and clinical assessment (including GRID-HAMD-17 and review of information) can occur in-person or remotely (via telephone/WebEx). When a participant opts to have questionnaires done remotely, they will receive the electronic version of the questionnaires by email or CAMH secure file transfer. The participant could complete the questionnaires electronically or print and fill in the questionnaires, and email (when completed directly electronically or when completed in the paper form then scanned), mail, or fax (when completed in the paper form) the completed questionnaires back to the study team. If participants choose to return the questionnaires by mail, we will provide a pre-paid postage envelope. The following procedures will be performed and recorded at the Baseline visit (V2):

- Administered by trained study staff:
  - Vital Signs (blood pressure, heart rate)
  - Urine drug screening & Pregnancy test
  - CGI
  - Brain MRI (required)
  - Avoid/Escape Go/No-Go task
  - UKU Side Effect Scale
  - Self-rated questionnaires: BDI-II, ASA-A, SHAPS, RRS-10, INQ-15, ISQ-8, GAFS-8, CD-RISC 10, ABSI, AAQ-II, WHOQOLY-4, SBQ-ASC, CFI
- Clinician administered:
  - GRID-HAMD-17
  - Confirmation of eligibility criteria
  - Review of assessments administered
  - Review of medications
- 2-hour preparatory session with the study therapists, which will involve building a therapeutic alliance, psychoeducation about the psychedelic experience, and setting intentions for the intervention.
  - Note: Therapists will have the option to schedule an additional preparatory session at their discretion.
  - For a more detailed explanation of the preparatory therapy session, please refer to the Yale Manual for Psilocybin-Assisted Therapy of Depression.
  - Prep therapy can occur in-person or via secure videoconferencing software (i.e. WebEx).

### ***Visit 3 (V3) – Safety Dose / Day -7***

The intervention will occur the day after Baseline (V2). The participant may have this session  $\leq 7$  days following the Baseline visit (V2). If the participant is out of the  $\leq 7$  day

window, all baseline assessments are to be repeated. On the day of the intervention the following procedures will take place:

- Study intervention administration (Section 5.0): 1 oral dose of 10 mg of psilocybin administered in conjunction with supportive therapy (PAT).
- Vital signs (blood pressure and pulse) will be taken every 1.5 hours during this session.
- At least one therapist will be present in the room at all times during PAT and be available to respond to participants' physical and emotional needs.
- Participants will be instructed to lie on a bed in a non-clinical environment, and therapists will encourage participants to focus their attention inward and stay with any experience that arises. To enhance inward reflection, a pre-selected music playlist will be played. Administration of questionnaires or other instruments to be completed at the end of the dosing session when the acute effects of psilocybin have resolved:
  - Study team or therapist administered:
    - 11D-ASC to assess the acute drug effects
    - UKU Side Effect Scale
- The participant will be discharged 6-8 hours post-dosing when, in the opinion of the study PI (or delegate), the acute effects of psilocybin are resolved. The participant must be accompanied home by a caregiver who will remain with them for up to 24 hours after the dose was administered.
- Rescue medications are permitted during this visit as outlined in Section 5.6.

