## **3.2 Primary Endpoints**

The primary safety endpoints of the main clinical trial design will be evaluated using standardized adverse events monitoring at all time points. Adverse event monitoring will be prioritized to closely and thoroughly evaluate the acute and sub-acute psychological safety profile. Blood pressure and heart rate will be examined before (V2) and during the psilocybin dosing sessions (V3/V4). Constant observation by therapists will monitor for adverse events during the dosing sessions. An on-call psychiatrist will be available at all times to further assess as needed for acute concerns. The safety endpoint is the number and severity of adverse events reported throughout the duration of the trial.

Feasibility endpoints of the main clinical trial design include the recruitment and retention rates. Dropout rates during three periods will be evaluated, namely: 1) screening period in which the participant undergoes medication tapering and washout; 2) during the acute course of the study intervention; and 3) during the follow-up after the intervention. Throughout all three periods, we will also evaluate adverse events including psychological distress and serious adverse events (e.g., hospitalization, suicide attempt, death).

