## **5.4 Administration of Study Intervention**

The IP will be prepared by the CAMH pharmacy and picked up by a trained research staff member. The IP will be given to the participant by a licensed physician who will supervise the participant. The participant will receive a capsule containing either 10mg or 25mg of psilocybin, depending on the visit. The capsules will be taken orally, with water. The capsules should not be opened or chewed.

After taking the IP, the participant will lie down on a bed in a non-clinical environment. Therapists will encourage participants to focus their attention inward and stay with any experience that arises. To enhance inward reflection, a pre-selected music playlist will be played quietly. Two study therapists trained in PAT will be supporting each participant during the dosing session with at least one therapist being present at all times to respond to the emotional and physical needs of the participant. Constant observation by therapists will monitor for adverse events during the dosing sessions. At least one member of the therapist pair will be a clinician. An on-call psychiatrist will be available at all times to further assess as needed for acute concerns.

The effects of psilocybin usually start about 20 to 30 minutes after administration, becoming the most intense in the first 90 to 120 minutes and gradually subsiding in 5 to 6 hours. The participants will be asked to remain in the room for the duration of the session regardless of the intensity of the effects, preferably lying down and mostly silent unless they have a concern or need to communicate a discomfort or seek reassurance from the therapist, or use the restroom. The therapists will 'check-in' with the participant (i.e., ask how the participant is doing) in 30-to-60 minute intervals post-dosing. A light meal and fruit will be available for the participant for lunch.

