### Rescue Medication

The decision to medicate a participant will depend on if the therapists and study investigator determine the safety of the patient and others can be maintained without medical intervention. The final decision will be made by the study investigator.

- Benzodiazepine anxiolytics
  - The preferred pharmacological intervention of choice in case of acute psychological distress (e.g. medications such as lorazepam or alprazolam that have a rapid onset, a short time until peak plasma concentration, and a short duration of therapeutic action).
  - The oral route is preferable because IV injection procedures may further exacerbate the participant's anxiety.
- Antipsychotic medications (e.g. risperidone) should be available in the event that an adverse reaction escalates to unmanageable psychosis.
- Management of blood pressure:
  - Asymptomatic with blood pressure (BP) < 180/100
    - Reassure, ensure lights are dim or off, tilt head of bed 15 degrees up and continue to monitor
    - Increase blood pressure measurement frequency to q15min until BP has partly normalized (sBP = 100-159; dBP = 60-99)
  - Asymptomatic with BP <180/100 for >30 minutes
    - Administer captopril\* 12.5mg PO/SL x 1 with MD order

- Increase blood pressure measurement frequency to q15min until BP has partly normalized (sBP = 100-159; dBP = 60-99)
- Asymptomatic with BP persisting at >180/100 for >60 minutes post-dose, despite administering first captopril dose:
  - Consider potential transfer to ER – decision to be made by study investigator
  - Administer 2nd dose of captopril 12.5mg x 1 with MD order
- Management of severe treatment emergent hypertension:
  - Consider potential transfer to ER – decision to be made by study investigator
  - Administer captopril 25mg PO/SL x 1
  - Call 911 immediately for patients experiencing symptoms of a hypertensive crisis (e.g., chest pain, shortness of breath) or hypertensive encephalopathy (e.g., sudden severe headache, visual disturbances, seizures, diminished consciousness, or focal neurological deficit)
- Note: if there are contraindications to captopril, substitute for hydralazine 10mg PO

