## 6.2 Schedule of Events

### 6.2.1 Main Clinical Trial

| Procedures   | Screening Visit (V1) | Tapering Period (2-4 weeks) | Baseline Visit 2 (V2, Day -15 to Day -8) | Safety Dose (V3, Day -7) | Treatment Dose (V4, Day 0) | Study Visit 5 (V5, Day 1) | Study Visit 6 (V6, Week 1) | Study Visit 7 (V7, Week 2) | Study Visit 8 (V8, Week 4) | Study Visit 9 (V9, Week 12) |
|---|-----------------------------|--|---|---------------------------------|-----------------------------------|----------------------------------|-----------------------------------|-----------------------------------|-----------------------------------|------------------------------------|
| Location of Visit   | Clinic                      | Remote or Clinic                               | Clinic  | Clinic                          | Clinic                            | Clinic                           | Remote or Clinic                  | Remote or Clinic                  | Remote or Clinic                  | Remote or Clinic                   |
| Allowable Window  |                             | Weekly   |   | Within 7 days following V2      | Within 7-10 days following V3     | None                             | ±3 days                           | ±3 days                           | ±3 days                           | ±3 days                            |
| Informed consent  | X                           |  |   |                                 |                                   |                                  |                                   |                                   |                                   |                                    |
| Demographics  | X                           |  |   |                                 |                                   |                                  |                                   |                                   |                                   |                                    |
| Medical history   | X                           |  | X   |                                 |                                   |                                  |                                   |                                   |                                   |                                    |

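### At V3 and V4 routine blood pressure is read only every 1.5 hours, with no stated pre-dose reading that day, so a silent rise under 90 minutes can go unread

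*Protocol*

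**What the plan says.** The V3 (10 mg) and V4 (25 mg) lists in Protocol section 6.1.2.1 carry the same instruction: "Vital signs (blood pressure and pulse) will be taken every 1.5 hours during this session". Neither list says when the first reading falls relative to the capsule, and neither names a reading before it is given. The Schedule of Events (6.2.1) only marks vital signs at these visits.

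Section 3.2 says "Blood pressure and heart rate will be examined before (V2) and during the psilocybin dosing sessions (V3/V4"), so the reading before dosing is assigned to V2. The visit windows in 6.2.1 are "Within 7 days following V2" for V3 and "Within 7-10 days following V3" for V4.

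The rescue part of section 5.6 has a ladder for raised blood pressure without symptoms. One step is "Increase blood pressure measurement frequency to q15min until BP has partly normalized". The captopril step is headed "Asymptomatic with BP <180/100 for >30 minutes". The printed sign looks reversed, since a raised value seems to be meant, but that is a separate matter and does not affect the timing discussed here.

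Section 5.4 describes the drug's time course: "The effects of psilocybin usually start about 20 to 30 minutes after administration, becoming the most intense in the first 90 to 120 minutes". It also provides for therapists to "ask how the participant is doing) in 30-to-60 minute intervals post-dosing", alongside constant observation.

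**The concern.** A rise in blood pressure without symptoms is found only by measuring it. The check-ins in 5.4 are verbal and the observation is visual, so neither would show it. The 5.6 ladder treats asymptomatic elevations of about half an hour as worth acting on, yet it depends on a routine reading to start it, and those readings are 90 minutes apart.

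This is a Phase I trial, and section 1.4 states that, to the investigators' knowledge, psilocybin has not been trialled in autistic people before. Describing acute safety is a main purpose. A rise that falls between readings is neither managed nor available to be judged as an adverse event. Without a stated same-day value before the capsule, a raised reading during the session is also harder to attribute to the dose.

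**Working it through.** The 90-minute interval is a design choice, so there is no derived figure in the protocol to reproduce. The check is interval arithmetic.

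**Inputs.** Routine interval I = 90 minutes (6.1.2.1, V3 and V4). Escalated interval 15 minutes and captopril after more than 30 minutes (5.6). Onset at 20 to 30 minutes and greatest intensity at 90 to 120 minutes (5.4). Check-ins every 30 to 60 minutes (5.4). Session length 6 to 8 hours. V3 up to 7 days after V2, and V4 7 to 10 days after V3 (6.2.1). 20 participants with two sessions each, so 40 sessions.

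**1. Limits that need no assumption about timing.** A rise of duration D can lie wholly between two readings whenever D < I, so the longest rise that can go unread is just under 90 minutes. A rise with D ≥ I is always read, at most I = 90 minutes after it began.

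**2. Effect on the 5.6 ladder.** If the 30-minute clock starts at the first raised reading, which is the natural interpretation, the first captopril dose for a persisting rise can come about 90 + 30 = 120 minutes after onset.

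**3. If readings are timed from dosing (assumption).** They fall at 90, 180, 270 and 360 minutes, plus 450 in an 8-hour session, which is 4 to 5 per session. No value is taken while effects begin and build, and one is taken at the very start of the 90-to-120-minute window. For example, a rise from minute 95 to minute 175 lasts 80 minutes, covers most of that window and is never read.

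**4. Illustration with onset uniform relative to the readings (assumption).** P(unread) = max(0, 1 − D/90):

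- D = 30: 1 − 30/90 = 67%
- D = 45: 1 − 45/90 = 50%
- D = 60: 1 − 60/90 = 33%
- D = 75: 1 − 75/90 = 17%
- D ≥ 90: 0%, with mean delay 90/2 = 45 minutes

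**5. Age of the stated earlier reading.** Before V3 it is the V2 reading, up to 7 days old. Before V4 the latest readings are those from the V3 session, 7 to 10 days old.

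**6. A dose-timed alternative.** Readings pre-dose and at 30, 60, 90, 120, 180, 270 and 360 minutes (450 if the session runs to 8 hours) make 8 to 9 per session. Any rise that starts within the first 120 minutes and lasts at least 30 minutes is then read within 30 minutes of onset. The largest gap is 60 minutes from 120 to 180, and 90 minutes afterwards as now. The added readings are pre-dose, 30, 60 and 120, so 4 per session and 4 × 40 = 160 in total. If a time-zero reading is already taken in practice, 3 are added, giving 3 × 40 = 120.

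**The case against.** The strongest objection is that every intermittent schedule misses rises shorter than its interval, and nothing in the protocol requires a shorter one. That is correct. The 30-minute spacing is a proposal, and what can be criticised is that readings are not tied to dosing and leave onset and peak thinly covered.

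Several further points stand in whole or in part:

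- **The percentages are illustrative.** Uniform onset fits poorly with 5.4, which times effects from dosing. A dose-timed schedule does read at minute 90. Section 5.4 also describes drug effects generally, so treating 90 to 120 minutes as the blood-pressure peak is inference. The 90-minute limits do not depend on either point.
- **Earlier detection does not always mean drug treatment.** A 30-minute rise would get no captopril under 5.6 even if found at once. The gain for short rises is closer monitoring and a recorded value. Earlier treatment applies to rises that persist.
- **Blood pressure is not itself the endpoint.** A reader might infer from 3.2 that unread rises are lost primary-endpoint data. The same section defines the safety endpoint by how many adverse events are reported and how severe they are. Blood pressure is a monitoring input to that, and a brief silent rise is not automatically an adverse event.
- **A time-zero reading may be implied.** The 1.5-hour instruction does not exclude one, and V2 is ideally the day before V3. The vital-signs row in 6.2.1 carries a footnote marker whose printed note concerns laboratory tests, so some detail may have dropped out. Even so, the text places the earlier reading at V2, and a time-zero value would leave every 90-minute gap in place.
- **Other safeguards lower the risk.** Uncontrolled hypertension and labile or low pressure are excluded (4.4.2), 10 mg precedes 25 mg, one of the two therapists is a clinician, and extra readings on clinical grounds are not barred. None of these is a scheduled measurement.

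**Conclusion.** The point holds as a first-detection gap. As written, an asymptomatic rise of anything under 90 minutes can pass unread at V3 or V4, a longer one can be found up to 90 minutes late, and no reading before the capsule is stated for either dosing day. These limits follow from the interval alone. The minute-90 and minute-180 timing assumes readings counted from dosing, and the miss probabilities assume uniform onset.

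Two stronger readings are tempting and not supported. A reader might infer that the 1.5-hour interval contradicts 5.6. It does not, because the ladder's clock can reasonably start at the first raised value, and the two sections can be followed together. A reader might also add the windows (7 + 10 = 17 days) and conclude that the 25 mg dose may be given on a 17-day-old blood pressure. That overlooks the V3 session, which supplies readings 7 to 10 days before V4.

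Neither the harm nor the number of participants affected can be computed, because the protocol gives no blood-pressure time course and no frequency of excursions. The change is worth making because it is cheap and serves a main purpose of the trial. Confidence is moderate for that reason.

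**What to change.** In the V3 and V4 lists of section 6.1.2.1:

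- require blood pressure and pulse on the dosing day before the capsule is given;
- time all later readings from dosing;
- add readings through onset and peak, for example at 30, 60, 90 and 120 minutes, taken at the 5.4 check-ins;
- then return to every 1.5 hours (180, 270 and 360 minutes, and 450 if the session runs on), and keep the 5.6 escalation unchanged.

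Amend the sentence in 3.2 to name the same-day pre-dose reading. The investigators may choose another interval, provided it covers onset and peak.

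The cost is a few lines of text and about 160 cuff readings over the trial, taken by staff already in the room. The real downside is interruption while participants are asked to be mostly silent and inward-focused. With check-ins every 30 minutes there is no new contact in the first two hours. With hourly check-ins, minutes 30 and 90 are additional, and minute 90 is already a reading if the present schedule is timed from dosing. Because autistic self-advocates endorsed the design (3.1), they should be asked whether the extra readings are acceptable.
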